5.4.5.2. Antihypertensive Medication

As infusion related reactions may include hypotension, the investigator should consider withholding antihypertensive treatments for 12 hours prior to and throughout each obinutuzumab infusion and for the first hour after completion of the infusion.

5.5. Accountability for Tirabrutinib, Idelalisib, and Obinutuzumab

The investigator is responsible for ensuring adequate accountability of all used and unused study drug bottles. This includes acknowledgement of receipt of each shipment of IMP (quantity and condition). All used and unused IMP bottles dispensed to subjects must be returned to the site.

Tirabrutinib, idelalisib, and obinutuzumab accountability records will be provided to each study site to:

- Record the date received and quantity of IMP bottles and vials
- Record the date, subject number, subject initials, and the quantity of IMP bottles and vials dispensed
- Record the date, quantity of used and unused IMP bottles returned, along with the initials of the person recording the information.

5.5.1. Investigational Medicinal Product Return or Disposal

Study drug should be retrieved from each subject at the end of each dispensing interval. The quantity of study drug and the date returned by the subject should be recorded in the study drug accountability records. All study drug returned by the subject should be retained for review by the study site monitor prior to destruction.

Please see Section [9.1.7](#) for more information.

6. STUDY PROCEDURES

The study procedures to be conducted for each subject enrolled in the study are presented in tabular form in [Appendix 2](#) and described in the text that follows.

The investigator must document any deviation from protocol procedures and notify the sponsor or contract research organization (CRO).

The study steering committee, including representatives from the GCLLSG and Gilead, will meet at least monthly throughout the treatment period and regularly for the complete duration of the study to review ongoing safety data.

6.1. Subject Enrollment, Randomization and Treatment Assignment

It is the responsibility of the Investigator to ensure that each subject is eligible for the study before enrollment or randomization. Please refer to Section [5.1](#) for details about randomization and treatment assignment. With Amendment 3, all subsequent subjects will be enrolled in Arm B.

6.2. Study Procedure Descriptions

During the treatment period, all visits may be performed within the specified window for that study visit (see [Appendix 2](#)).

6.2.1. Informed Consent

All subjects must sign and date the most recent IEC approved informed consent form before any study procedures are performed. **CCI**

Subjects who screen fail must re-sign the informed consent, if any screening procedures will be performed outside of the 28-day screening window from the time of the first informed consent.

6.2.2. Medical and Medication History

A complete medical history will be obtained by the Investigator or designee. Medical history will include information on the subject's significant past medical events (eg, prior hospitalizations or surgeries), a review of the disease under study, prior anti-cancer therapies, and any concurrent illnesses. CIRS score should be determined at screening.

6.2.3. Physical Examination

The Investigator or qualified designee will perform a physical examination at screening and time points outlined in the Study Procedures Tables ([Appendix 2](#)). Screening and End of Treatment (EOT) will be a complete physical examination. Beginning at Week 1 Day 1, a modified physical examination will be performed to monitor for any changes (lymph nodes, size of liver and spleen, lung, cardiac, abdomen, skin, neurologic, and any systems, as clinically indicated). Physical examination findings will either be reported as medical history or AEs based on the requirements in Section 7.

Weight should be measured with each physical examination.

Height will be measured at screening only.

6.2.4. Vital Signs

Vital signs, including blood pressure, respiratory rate, pulse, and temperature will be measured at the time points listed in the Study Procedures Tables in [Appendix 2](#). Only the screening measurements will be recorded on the appropriate eCRF page with appropriate source documentation. Any abnormal measurements may be repeated and reported as AEs if appropriate. All measures of blood pressure will be performed using standard sphygmomanometry. Measurements of blood pressure should be taken per institutional guidelines.

6.2.5. ECOG Performance Status/B-Symptoms

ECOG PS and B-Symptoms will be performed at the time points listed in the Study Procedures Tables ([Appendix 2](#)). ECOG will be scored using the scale index in [Appendix 5](#).

6.2.6. 12-lead ECG

A 12-lead ECG will be obtained at the time points listed in the Study Procedures Table ([Appendix 2](#)).

6.2.7. Binet and Rai Staging

Binet and Rai staging will be assessed at the time points listed in the Study Procedures Table ([Appendix 2](#)). CLL staging will be evaluated using the table in [Appendix 9](#).

6.2.8. Geriatric assessment

The G8 screening questionnaire ([Appendix 10](#)) will be used for assessment for subjects aged > 70 years as outlined in the Study Procedures Table ([Appendix 2](#)).

6.2.9. Prior and Concomitant Medications

At screening, all medication taken up to 30 days prior to the screening visit will be recorded on the eCRF. At each study visit, the site will capture any and all medications taken by the subject since the last visit or during the visit (as applicable). Concomitant medications include prescription and non-prescription medications, pre-infusion medications (eg, anti-emetics), and vitamins and minerals.

In addition, supportive therapies given during the course of the study (eg, blood transfusion, growth factor) should be collected and recorded on the eCRF.

6.2.10. Adverse Events

Subjects will be assessed for AEs per guidelines in the NCI CTCAE (version 4.03) at the time points outlined in the Study Procedures Tables ([Appendix 2](#)). After informed consent, but prior to initiation of study medication, the following types of events should be reported on the electronic case report form eCRF: AEs related to protocol-mandated procedures, and all SAEs.

Any AEs reported after informed consent is obtained and throughout the study will be recorded on the eCRF with appropriate source documentation. Please refer to [Appendix 3](#) for CTCAE grading criteria.

Please refer to Section [7](#) for additional information on AE reporting.

6.2.10.1. Evaluation for Gastrointestinal Events/Colitis

For subjects who report diarrhea or colitis, obtain history of onset and duration, including description of the number of stools and stool composition (watery, bloody, nocturnal), travel history, diet changes and medication review to identify possible causes. Perform physical examination, including assessment for fever, dizziness, abdominal pain/cramping, and weakness (ie, evaluate for sepsis, bowel obstruction, dehydration). If unclear, consider upper and lower tract endoscopy with biopsy. Laboratory evaluation for infectious causes of diarrhea should be performed and in the absence of a diagnosis, endoscopy should be considered with evaluation for CMV and other infectious pathology.

6.2.11. Radiology Assessment

The radiology assessment in this study is consistent with the European Society for Medical Oncology (ESMO) clinical practice guidelines for CLL {[Eichhorst 2015](#)}. Imaging of the neck, chest, abdomen and pelvis by CT scan (preferred) or MRI will be performed at screening. Scans already completed up to 42 days prior to the first dose of treatment may be used for the screening assessment. One additional radiologic evaluation is specified per protocol, at the Week 25 visit, with evaluation of areas affected by CLL during the screening evaluation. During the treatment phase, if an improvement in clinical response is noted following the Week 25 assessment or if disease progression is suspected, additional scans may be performed if clinically indicated. Scans should continue to be performed at Week 25 for subjects who stop study treatment but did not

have disease progression (e.g. experienced unexpected toxicity) unless radiographic progression is previously documented or unless the subject starts on subsequent therapy for CLL.

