4.2. Inclusion Criteria

Subjects must meet all the following criteria to be eligible for participation in this study:

- 1) Documentation of relapsed or refractory CLL
- 2) Have an indication per modified IWCLL 2008 criteria for treatment; subjects without radiographically measurable disease (defined as ≥ 1 lesion > 1.5 cm in diameter as assessed by CT or MRI) must have bone marrow evaluation at screening
- 3) Adequate hematologic function as indicated by a platelet count $\geq 50 \times 10^9/L$, a neutrophil count $\geq 1 \times 10^9/L$ and a hemoglobin ≥ 8 g/dL unless lower values are directly attributable to documented bone marrow burden of CLL
- 4) Adequate renal function as indicated by a CrCl ≥ 50 mL/min calculated by the modified Cockcroft-Gault formula or from a 24 hour urine collection
- 5) Adequate liver function as indicated by total bilirubin $\leq 1.5 \times$ institutional upper limit of normal (ULN) unless attributed to Gilbert's syndrome and AST/ALT $\leq 2.5 \times$ ULN
- 6) Male or female ≥ 18 years of age
- 7) Eastern Cooperative Oncology Group (ECOG) Performance Status (PS) ≤ 2
- 8) Absence of active HBV infection (serological testing within 6 weeks prior to randomization or enrollment with the following results: HBsAg negative AND anti-HBcAb negative, or if anti-HBcAb positive, HBV DNA PCR negative)
- 9) HCV Ab negative or if Ab positive, negative HCV RNA PCR within 6 weeks prior to randomization or enrollment
- 10) Negative testing for HIV within 6 weeks prior to randomization or enrollment
- 11) Satisfies the following criteria:
 - a) For female subjects of childbearing potential, willingness to abstain from sexual intercourse or use a protocol-specified method of contraception as described in [Appendix 4](#)
 - b) Male subjects of reproductive potential who engage in sexual intercourse must agree to use protocol-specified method(s) of contraception as described in [Appendix 4](#)

- 12) Ability and willingness to provide written informed consent and adhere to protocol requirements including study visit schedule, drug administration plan, imaging studies, laboratory testing, other study procedures and restrictions including mandatory prophylaxis for PJP

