4.3. Exclusion Criteria

Subjects who meet any of the following exclusion criteria are not eligible for participation in this study:

- Known transformation of CLL (ie, Richter's transformation, prolymphocytic leukemia)
- Known CNS involvement
- Progression on treatment with any inhibitor of BTK, SYK, PI3K, BCL-2, or obinutuzumab. The treatment and disease response history of subjects with prior treatment with agents in these classes should be reviewed by the sponsor or the GCLLSG study office centrally prior to enrollment to clarify sensitivity to these treatments.
- Any treatment for CLL other than corticosteroids for symptomatic management within 28 days of the start of study treatment
- Participation on a concurrent therapeutic clinical trial unless all treatment is complete with only ongoing surveillance
- Diagnosis of or concern for progressive multifocal leukoencephalopathy
- History of myelodysplastic syndrome or another malignancy other than CLL, *except* for the following: any malignancy that has been in complete remission for 3 years, adequately treated local basal cell or squamous cell carcinoma of the skin, cervical carcinoma in situ, superficial bladder cancer, asymptomatic prostate cancer without known metastatic disease and with no requirement for therapy or requiring only hormonal therapy and with normal prostate-specific antigen for ≥ 1 year prior to start of study therapy
- Active infection requiring systemic therapy
- Pregnant or nursing women (a negative pregnancy test is required for all women of childbearing potential within 7 days before start of treatment and monthly during therapy)
- Active autoimmune disease including autoimmune hemolytic anemia or idiopathic thrombocytopenic purpura requiring a higher corticosteroid equivalent than prednisone 10 mg daily. Higher doses of corticosteroids prescribed for any indication must be stopped >14 days prior to randomization or enrollment; exceptions may be made for corticosteroids prescribed specifically for management of CLL symptoms after discussion with the study medical monitor.

- Diagnosis of inflammatory bowel disease or ongoing symptomatic pneumonitis
- Ongoing CMV infection, treatment or prophylaxis for CMV within the past 28 days

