8.1.3. Secondary Endpoints

The secondary endpoints of this study are:

- Rate of CR/BM MRD- at Week 25
- Rate of CR/PB MRD- at Week 25
- ORR at Week 25 including CR, CRi, PR, and PR with lymphocytosis
- Type, frequency, and severity of AEs and SAEs

CCI

[REDACTED]

[REDACTED]

[REDACTED]

[REDACTED]

[REDACTED]

[REDACTED]

[REDACTED]

[REDACTED]

[REDACTED]

[REDACTED]

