14. CLL immunophenotyping, karyotyping and FISH, TP53 and IgHV mutation status, CD38 and ZAP70 expression will be evaluated from peripheral blood at screening. In the event of disease progression, only FISH and TP53 will be evaluated.
15. Tumor evaluation by CT scan (preferred) or MRI of neck, chest, abdomen, and pelvis will be performed at screening (unless scan was already completed up to 42 days prior to first dose). At the Week 25 visit, the same type of evaluation should be performed on those body regions which showed involvement by CLL at screening. An additional CT may be obtained on protocol per investigator discretion following evidence of an improvement in clinical response if the response assessment at the Week 25 visit is less than a complete response or in the event of suspected disease progression.
16. A bone marrow evaluation is required in the screening window for subjects without radiographic evidence of disease. Bone marrow aspirate and biopsy should be performed at Week 25 for subjects fulfilling clinical response criteria for CR or CRi per the modified IWCLL 2008 criteria. MRD should be assessed from bone marrow aspirate at the reference laboratory in Kiel; CCI [REDACTED]
CCI [REDACTED]
17. Qualitative treatment response assessment based on physical exam, laboratory parameters and presence of B symptoms should be performed every 4 weeks until Week 33 Day 1 and then at all scheduled visits thereafter following the modified IWCLL 2008 criteria, with the exception of lymphadenopathy, hepatomegaly, splenomegaly, and bone marrow. Assessment of response per modified IWCLL 2008 criteria should also be recorded at the completion of 24 weeks on treatment and subsequent to any CT and/or bone marrow biopsy that is repeated while on study.
18. Following evaluation of the safety data for the first 6 subjects enrolled in each treatment arm, the Safety Review Team (SRT) will determine if weekly clinical evaluation should continue for the duration of the study.
19. The EOT visit should be scheduled for approximately 30 days following discontinuation of all study treatment. For subjects that permanently discontinue all treatment prior to Week 25 Day 1, the Week 25 Day 1 visit should also be performed and may satisfy the requirement for the EOT visit if falling into the +30 days \pm 7 day window from all study drug discontinuation.

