Appendix 6. Modified IWCLL 2008 Response Criteria

The determination of CLL response and progression will be based on standardized International Workshop on CLL (IWCLL) 2008 criteria {Hallek 2008}, as specifically modified for this study to reflect current recommendations which consider the mechanism of action of small molecule targeted therapy {Cheson 2012}.

Complete remission (CR):

All below listed criteria must be fulfilled and no disease related symptoms should be present.

Complete remission with incomplete recovery of the bone marrow (CRi):

All below listed criteria must be fulfilled, except for an incomplete recovery of the bone marrow with persisting anemia, thrombocytopenia and/or neutropenia (related to toxicity of treatment and not due to CLL) and no disease related symptoms should be present.

Partial response (PR):

Among the below listed criteria at least 2 from group A and 1 from group B must be fulfilled.

Partial response with lymphocytosis (PR-L):

Among the below listed criteria at least 2 from group A and 1 from group B must be fulfilled, however, a lymphocytosis related to treatment may be present.

Nodular partial response (nPR):

All criteria for a CR/CRi are fulfilled, but the bone marrow shows lymphoid nodules. As in a lot of cases these nodules are related to bone marrow proliferation during recovery, efforts should be made to prove that these lymphocytes are no CLL cells by 4-colour-flow cytometry to be able to define these patients as CR/CRi. If this cannot be proved by either FACS or MRD from the bone marrow patients will be considered PR and therefore this category will not appear on the eCRF.

Stable disease (SD):

Failure to achieve a PR and absence of PD.

Progressive disease (PD):

Presence of at least 1 of the below enlisted criteria or appearance of new lymph nodes > 1.5 cm, hepato- or splenomegaly or organ infiltration by CLL.

Response criteria

Parameter	CR	CRi	PR	PR-L	PD
Group A (indicating tumor load)					
Lymphadenopathy ¹	none > 1.5 cm		decrease \geq 50%		increase by \geq 50% or new lymph nodes \geq 1.5 cm
Hepatomegaly	none		decrease \geq 50%		Increase by \geq 50 %
Splenomegaly	none		decrease \geq 50%		Increase by \geq 50 %
Blood lymphocytes	< 4000/ μ L		decrease of \geq 50% from baseline	increase	Increase by \geq 50% over baseline ² to \geq 5000/ μ L
Bone marrow	Normocellular	hypocellular	50% reduction in BM infiltrates ³		irrelevant
	30% lymphocytes, no B-lymphoid nodules				

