6.1. Primary Efficacy Endpoint

6.1.1. Definition of the Primary Efficacy Endpoint

The primary efficacy endpoint of this study is the rate of CR per modified IWCLL 2008 criteria {Hallek 2008} at Week 25, which is defined as the proportion of subjects who achieved CR/CRi at Week 25. Subjects who received anti-cancer therapy other than the study drug prior to achieving CR/CRi at Week 25, will be considered as nonresponders for CR/CRi and will be included in the denominator when calculating the CR rate at Week 25.

The analysis window of Week 25 response assessment is defined as $24 \times 7 \pm 28$ days (inclusive) starting from first dose. This analysis window is extended from the visit window to capture the assessments outside the scheduled window. If there are multiple assessments within the analysis window, records will be chosen based on rules specified in Section 3.8.3.

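### A baseline scan may be up to 42 days old while prior CLL treatment need stop only 28 days before first dose, so the baseline for PR, and hence for ORR, can predate the end of prior therapy

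*Protocol*

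**What the plan says.** On imaging, Protocol Section 6.2.11 says: "Scans already completed up to 42 days prior to the first dose of treatment may be used for the screening assessment". Footnote 15 of the procedures table (Protocol Appendix 2, repeated in SAP Appendix 1) gives the same allowance: tumor evaluation "will be performed at screening (unless scan was already completed up to 42 days prior to first dose". The only other imaging scheduled for every subject is at Week 25, where "the same type of evaluation should be performed on those body regions which showed involvement by CLL at screening".

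On prior therapy, Section 4.3 excludes "Any treatment for CLL other than corticosteroids for symptomatic management within 28 days of the start of study treatment".

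On response, Protocol Appendix 6 defines CR and CRi by fixed limits: no node above 1.5 cm, no enlarged liver or spleen, lymphocytes below 4000/µL, and marrow criteria. For PR, nodes, liver and spleen must each be judged on a decrease of at least 50%, under this rule: "Among the below listed criteria at least 2 from group A and 1 from group B must be fulfilled". PR-L follows the same rule but tolerates treatment-related lymphocytosis.

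On endpoints, SAP Section 6.1.1 takes the Week 25 CR rate as primary, "which is defined as the proportion of subjects who achieved CR/CRi at Week 25". PR and PR-L enter the secondary endpoint in Protocol Section 8.1.3, "ORR at Week 25 including CR, CRi, PR, and PR with lymphocytosis", and the best-response ORR added in SAP Section 6.4.

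**The concern.** The scan window is longer than the washout, and nothing ties the date of an accepted scan to the last dose of prior CLL treatment. A subject could be scanned on Day -40, receive prior treatment until Day -30, and start study drug with the Day -40 scan as baseline.

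For any endpoint built on change from baseline, the change then spans part of another therapy. If that therapy shrank nodes or spleen after the scan, the baseline is too high and some of the shrinkage is credited to study drug. If the scan caught disease while it was suppressed and it then regrew, the baseline is too low and a true PR is harder to reach. Either way the recorded response is not the response to study treatment alone. With no comparison between arms planned, nothing cancels the error.

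The screening scan also decides which body regions are imaged at Week 25. Disease that appears after a mid-therapy scan, in a region recorded as uninvolved, has no scheduled re-imaging.

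**Working it through.** **1. The plan's own precision figure.** SAP Table 1-1 gives 90% Clopper-Pearson limits at n = 30. Recomputed for 6, 9, 12, 15 and 18 responders: 9.1-35.7, 16.6-46.5, 25.0-56.6, 33.9-66.1 and 43.4-75.0. These match the table apart from the last upper limit (75.1 stated). The largest distance from estimate to limit is 16.6 points, inside the stated ±17.0.

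**2. The gap.** Oldest accepted scan: 42 days before first dose. Treatment-free interval: 28 days. 42 - 28 = 14 days, that is Day -42 to Day -29, in which an accepted scan can be followed by further prior treatment. A scan during the last regimen fits easily. A scan before the whole of it fits only if that regimen lasted about two weeks or less.

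**3. Effect on the PR threshold.** Let B be disease size on the scan. If prior therapy then shrinks it by a fraction f, size at first dose is B(1 - f). A 50% decrease from the scan needs B(1 - f)(1 - g) ≤ 0.5B, so the shrinkage required during study treatment is g = 1 - 0.5/(1 - f). If disease instead regrows by a fraction r, g = 1 - 0.5/(1 + r). The documents give neither f nor r; the values below are assumed.

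| Change between scan and first dose | Shrinkage required on study for PR |
|---|---|
| none | 50.0% |
| shrinks 10% | 44.4% |
| shrinks 20% | 37.5% |
| shrinks 30% | 28.6% |
| shrinks 40% | 16.7% |
| shrinks 50% | 0% |
| regrows 25% | 1 - 0.5/1.25 = 60.0% |
| regrows 50% | 1 - 0.5/1.50 = 66.7% |

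The error runs in both directions. Three of the five group A items (nodes, liver, spleen) are organ measurements, so two of them can satisfy the group A part of PR without the blood or marrow items.

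**4. Effect on CR/CRi.** No CR/CRi limit in Appendix 6 is a change from the baseline scan, so f and r do not enter and the percent-change effect is zero. The same holds for the CR component of the two CR/MRD-negative endpoints.

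**5. Scale.** One subject in 30 is 1/30 = 3.3 points. For illustration, 24/30 = 80.0% (90% CI 64.3-90.9) becomes 23/30 = 76.7% (60.6-88.5) if one PR is reclassified, and 21/30 = 70.0% (53.5-83.4) if three are. The documents do not report how many subjects had a scan in the 14-day gap or treatment after it.

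**The case against.** The strongest reply is that little of consequence is exposed.

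- The primary endpoint does not use change from baseline. This stands. Any carry-over of prior therapy into CR would come from the washout itself and would be the same with a fresh scan.
- Enrolled subjects must have relapsed or refractory disease and "Have an indication per modified IWCLL 2008 criteria for treatment", and selected screening data are reviewed before enrollment (Protocol Section 5.1). Someone whose nodes had just shrunk substantially is unlikely to qualify. This makes large carry-over less likely, but no criterion requires progression after the last therapy, and partial shrinkage is compatible with a continuing indication.
- PR also needs a group B item, and blood counts are taken on Day 1. True, but this does not correct the organ measurements.
- The baseline is the latest value before randomization (Protocol Section 8.3) or first dose (SAP Section 3.8.3), so a newer scan would take over. This does not help: the older scan stands in for the screening scan, so there is usually nothing newer to select.
- Time since the last regimen is summarized (SAP Section 5.4). That helps identify recent therapy, but no planned analysis links it to the scan date.

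A reader might infer that the gap lets residual disease pass as CR, because regions clear at screening are not re-imaged. The chain is possible but long. Disease must regrow in a region recorded as clear and stay above 1.5 cm while all imaged disease resolves. It must also be missed by the physical examinations on Day 1 and at Week 25, with a clear marrow and no disease-related symptoms. Restricting re-imaging to involved regions is, moreover, a separate choice that exists with a fresh scan too.

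**Conclusion.** The gap is real and unaddressed: for 14 days, an accepted baseline scan can predate the end of prior CLL treatment. Its direct effect is confined to PR and PR-L, hence to Week 25 ORR and the SAP's best-response ORR. Severity is minor.

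Three stronger readings are tempting but not supported:

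- That prior-therapy effect is counted in the primary CR rate. The CR/CRi limits are absolute; only the indirect coverage route remains.
- That the bias can only inflate response. Regrowth after the scan raises the threshold for PR and lowers ORR, so the net sign is undetermined.
- That a particular number of subjects is affected. None is given. The per-subject figure of 3.3 points is arithmetic at n = 30, and the one and three reclassified responders above are illustrations.

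The conclusion rests on reading the two windows as written and on no unstated site practice requiring a post-therapy scan. Whether a scan on study day -40 with treatment to Day -30 ever occurred can be answered only from the data.

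**What to change.** In Protocol Section 6.2.11 and footnote 15 (Protocol Appendix 2 and SAP Appendix 1), state that an existing scan older than 28 days may serve as baseline only if it was obtained after the last dose of any prior CLL treatment, corticosteroids for symptoms excepted. Otherwise the already scheduled screening scan is performed in the Day -28 window, which by the exclusion criterion follows prior treatment.

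If enrolment is complete, amend the SAP to list baseline scan date against last prior dose for each subject, and repeat both ORR analyses with affected PR and PR-L subjects counted as non-responders. Two cautions apply. This repeat guards only against upward error; it does not restore a PR missed through regrowth. Also, SAP Section 5.4 imputes a completion date with a missing day to the first of the month (the Section 5.3 rule), which can move the end of therapy to before the scan and hide an overlap, so such subjects should be flagged as undetermined.

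The cost is one sentence, plus a listing and a repeat analysis if needed. A subject whose only older scan predates the last prior dose loses its use and has the scheduled scan. Sample size and the interval table do not change. The condition does not remove delayed effects of a therapy that ended shortly before the scan, nor the effect of exempt corticosteroids; it ensures only that no other prior CLL treatment was given after the baseline.
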